5.5.1.2. Modification of Study Drug

The number and percentage of patients with at least one dose interruption along with reason for the interruptions will be summarized by cohort and study drug.

The number and percentage of subjects with at least one dose reduction and reason for the dose reduction will be summarized by cohort and study drug.

The number and percentage of subjects with at least one dose discontinuation and reason for the dose discontinuation will be summarized by cohort and study drug.

By-patient listings of dose interruption, dose reduction and dose discontinuation will be also provided.

5.5.2. Adverse Events

5.5.2.1. Deaths

On-treatment deaths and reasons for death will be summarized.

A by-patient listing of all deaths occurring during screening, on-treatment, or survival follow-up periods will be provided.

5.5.2.2. Adverse Events

AE is any untoward medical condition that occurs in patients while participating in this clinical study. Adverse events will be coded according to the MedDRA (the most up-to-date version at the time of analysis) terminology and the severity of the toxicities will be graded according to NCI CTCAE (Version 5.0), where applicable.

An on-treatment AE is defined as an AE that is starting or worsening at the time of or after the first dose of study drug administration and within 30 days after the last dose of study drug, and do not necessarily have a causal relationship to the use of the study drug. All AEs captured in the database will be listed; however, only on-treatment AEs will be summarized.

The following AE summary tables will be generated:

- 1) Summary of AEs with the number and percentage of patients reporting AEs, serious AEs, grade ≥ 3 AEs, AEs leading to study drug discontinuation, interruption and dose reduction, and AEs with outcome of deaths.
- 2) Summary of treatment-related AEs with the number and percentage of patients reporting AEs, serious AEs, grade ≥ 3 AEs, AEs leading to study drug discontinuation, interruption and dose reduction, and AEs with outcome of deaths.
- 3) Summary of AEs by worst CTCAE Grade (grade 1, 2, 3, 4, 5, any grade, Grade ≥ 3) presented by System Organ Class (SOC) and Preferred Term (PT).
- 4) Summary of treatment-related AEs by worst CTCAE grade (Grade 1, 2, 3, 4, 5, any grade, Grade ≥ 3) presented by SOC and PT.
- 5) Summary of AEs leading to death by SOC and PT.
- 6) Summary of the most common AEs ($\geq 10\%$ incidence) and median time to first AE by SOC and PT.

5.5.2.3. Adverse Events Leading to Discontinuation of Study Drug

AEs leading to discontinuation will be summarized:

- Summary of AEs leading to discontinuation of study drug by worst CTCAE Grade (grade 1, 2, 3, 4, 5, any grade, Grade ≥ 3) presented by SOC and PT
- Summary of treatment-related AEs leading to discontinuation of study drug by worst CTCAE grade (Grade 1, 2, 3, 4, 5, any grade, Grade ≥ 3) presented by SOC and PT

A by-patient listing of AEs leading to discontinuation of study drug will also be provided.

5.5.2.4. Adverse Events Leading to Dose Modification of Study Drug

AEs leading to dose modification (including dose interruption and reduction) of study drug will be summarized:

- Summary of AEs leading to dose modification of study drug by worst CTCAE Grade (grade 1, 2, 3, 4, 5, any grade, Grade ≥ 3) presented by SOC and PT

- Summary of treatment-related AEs leading to dose modification of study drug by worst CTCAE grade (Grade 1, 2, 3, 4, 5, any grade, Grade ≥ 3) presented by SOC and PT

A by-patient listing of AEs leading to dose modification of study drug will also be provided.

5.5.2.5. Serious Adverse Events

Serious adverse event (SAE) will be summarized:

- Summary of SAEs by worst CTCAE Grade (grade 1, 2, 3, 4, 5, any grade, Grade ≥ 3) presented by SOC and PT
- Summary of treatment-related SAEs by worst CTCAE Grade (grade 1, 2, 3, 4, 5, any grade, Grade ≥ 3) presented by SOC and PT

A by-patient listing of SAEs will also be provided.

5.5.2.6. Adverse Events of Special Interest

Incidence

AESI will be summarized:

- Summary of AESI with the number and percentage of patients reporting AESI, serious AESI, grade ≥ 3 AESI, AESI leading to study drug discontinuation, interruption and dose reduction, and AESI with outcome of deaths.
- Summary of AESI by worst CTCAE grade (grade 1, 2, 3, 4, 5, any grade, Grade ≥ 3) presented by category or subcategory / PT

A by-patient listing of AESI will also be provided.

Time to Onset

Time-to-onset of selected AESI (e.g. hyperphosphatemia) will be summarized for each category/subcategory of AESI.

- Time-to-onset of any grade AESI
- Time-to-onset of Grade ≥ 3 AESI

Time-to-onset analyses are restricted to treated patients with at least one specific event.

The derivation of time-to-onset of AESI is detailed in Section 6.4.

Time to Resolution

Time-to-resolution of selected AESI (e.g. hyperphosphatemia) will be summarized.

- Time-to-overall resolution of AESI
- Time-to-resolution of Grade ≥ 3 AESI (overall and until \leq Grade 2)

The following summary statistics will be reported: percentage of subjects who experienced the specific events, percentage of subjects with resolution of the AESI (clustered), median, 1st quartile and 2nd quartile of time-to-resolution along with 95% CI (derived from Kaplan-Meier estimation) and ranges.

Time-to-resolution of Grade ≥ 3 AESI (e.g. hyperphosphatemia) will be graphically displayed using the Kaplan-Meier technique.

Time-to-resolution analyses are restricted to patients who experienced the specific events. Collapsing selected AE and derivation of time-to-resolution of AESI is detailed in Section 6.5.

5.5.2.7. Multiple Events

The following summary tables will be provided:

- A table showing the total number and rate (exposure adjusted) of occurrences for all AEs by SOC and PT
- A table showing the total number and rate (exposure adjusted) of occurrences for AESI by category / subcategory

The exposure adjusted incidence rate per X patient time is calculated as $X \times Y \times (\text{total number of unique AEs}) / (\text{total exposure time})$, where:

X = user-specified time factor, X= 1000 or 100

Y = 365.25 for years or Y = 30.4375 for months

For example, Incidence rate (IR) per 100 person-years of exposure (IR/100 P-Y) is calculated as $100 \times 365.25 \times (\text{total number of unique AE count}) / (\text{total exposure time in days})$.

Unique instances of all AEs (that is, after duplicates have been eliminated and overlapping and contiguous occurrences of the same event (same PT) have been collapsed) will be summarized (0 event, 1 event, 2-3 events, ≥ 4 events) by PT. Unique instances of AESI will be summarized (0 event, 1 event, 2-3 events, ≥ 4 events) by category/subcategory.

Unique instances of all AEs will be listed.

The algorithm of collapsing selected AE records is detailed in Section 6.6.

5.5.3. Clinical Laboratory Evaluations

Clinical laboratory results will be summarized using SI units. Laboratory measurements will be summarized for each parameter. Descriptive statistics (n, mean, standard deviation, median, minimum and maximum) will be presented for clinical chemistry, hematology and coagulation parameters at each scheduled visit. Change from baseline will be summarized in a similar manner.

Laboratory test results will be graded by NCI CTCAE (Version 5.0). Shift tables will be presented for each laboratory parameter to display the shift from baseline grade to the worst post-baseline grade. Summary tables will be provided presenting the number and percentage of patients for each laboratory test by baseline grade and worst post-baseline grade. All post-baseline assessments (including unscheduled visits) will be used to determine the worst post-baseline grade. Time to maximum Grade 3/4 and time to resolution (return to grade ≤ 2 or baseline grade or below) may be summarized as appropriate.

All clinical laboratory data will be presented in by-patient listings.

The laboratory tests of Hematology, Coagulation, Serum chemistry are listed in Table 11.

Table 11. Laboratory Tests

Assessment	Test Items
Hematology and Coagulation	Red blood cell count, Hemoglobin, Hematocrit, Platelet count, White blood cell count with differential (Absolute neutrophil count, Lymphocytes, Monocytes, Eosinophils, Basophils), Prothrombin time-international normalized ratio, Activated partial thromboplastin time, Fibrinogen
Chemistry (Serum or plasma)	AST, ALT, ALP, Total bilirubin, Direct bilirubin, Albumin, Lactate dehydrogenase, phosphate, Triglyceride, Total cholesterol, Creatinine, Urea or blood urea nitrogen, Sodium, Bicarbonate, Potassium, Chloride, Magnesium, Calcium (corrected value), Blood glucose, Creatinine clearance (if there is a measured value, use the measured value), estimated glomerular filtration rate

For a calculated creatinine clearance (Ccr) value, use the Cockcroft-Gault formula:

Male Ccr (mL/min) = weight (kg)×(140-age(years))/[72×serum creatinine (mg/dL)]

Female Ccr (mL/min) = male Ccr×0.85

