4. SELECTION AND WITHDRAWAL OF PATIENTS

4.1. Inclusion Criteria

A patient must meet all of the following criteria to be eligible for participation in this study; waivers will not be granted for any of the eligibility criteria.

1. Histologically confirmed advanced or metastatic UC in patients who have not received systemic treatment for advanced metastatic disease. For patients who received prior adjuvant/neoadjuvant chemotherapy or chemo-radiation for urothelial carcinoma, a treatment-free interval >12 months between the last treatment administration and the date of recurrence is required in order to be considered treatment-naïve in the metastatic setting.
 - a. In safety lead-in: enrollment regardless of FGFR status
 - b. Cohort A: must have an *FGFR3* mutation or *FGFR1-4* fusion/rearrangement
 - c. Cohort B: all other patients with UC (including patients with other FGFR or non-*FGFR* genetic aberrations and patients with WT [nonmutated] tumors)
2. Unfit for or intolerant to standard platinum-based chemotherapy as defined by any one of the following criteria:
 - a. Chronic kidney disease characterized by the estimated creatinine clearance rate (eCCr) per Cockcroft-Gault formula of <60 mL/min or estimated glomerular filtration rate (eGFR) of <60 mL/min/1.73 m², corresponding to NCI-CTCAE v.5.0 Grade ≥ 2
 - b. Impaired hearing (measured by audiology) of >25 dB at two contiguous test frequencies in at least one ear, corresponding to NCI-CTCAE v.5.0 Grade ≥ 2
 - c. Peripheral sensory neuropathy Grade ≥ 2 by NCI-CTCAE v.5.0
 - d. Patient refusal
 - e. In the opinion of the Investigator, the patient is considered ineligible to receive any platinum-based chemotherapy
3. Be willing and able to provide written informed consent for the trial.
4. Be ≥ 18 years of age.
5. Have an Eastern Cooperative Oncology Group (ECOG) performance status (PS) of 0 to 1.
6. Adequate organ function as defined by the following criteria:
 - a. Absolute neutrophil count (ANC) $\geq 1.5 \times 10^9/L$
 - b. Platelet count $\geq 100,000/mm^3$
 - c. Hemoglobin $\geq 9.0 \text{ g/dL}$
 - d. Alanine aminotransferase (ALT) and aspartate aminotransferase (AST) $\leq 2.5 \times$ upper limit of normal (ULN); if liver function abnormalities are due to underlying liver metastasis, AST and ALT $\leq 5.0 \times$ ULN.

- e. Total bilirubin $\leq 1.5 \times$ ULN, or $\leq 3.0 \times$ ULN for patients with Gilbert's syndrome.

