Diarrhea / Colitis	Grade 2 or 3	Withhold	
 Administer corticosteroids (initial dose of 1-2 mg/kg prednisone or equivalent) followed by taper 	
 Monitor patients for signs and symptoms of enterocolitis (ie, diarrhea, abdominal pain, blood or mucus in stool with or without fever) and of bowel perforation (ie, peritoneal signs and ileus). Patients with \geq Grade 2 diarrhea suspecting colitis should consider GI consultation and performing endoscopy to rule out colitis. Patients with diarrhea/colitis should be advised to drink liberal quantities of clear fluids. If sufficient oral fluid intake is not feasible, fluid and electrolytes should be substituted via I.V. infusion.
	Recurrent Grade 3 or Grade 4	Permanently discontinue		

irAEs	Toxicity grade or conditions (CTCAE V5.0)	Action with pembrolizumab	Corticosteroid and/or other therapies	Monitoring and follow-up
AST or ALT elevation or Increased Bilirubin	Grade 2 ^a	Withhold	
 Administer corticosteroids (initial dose of 0.5-1 mg/kg prednisone or equivalent) followed by taper 	
 Monitor with liver function tests (consider weekly or more frequently until liver enzyme value returned to baseline or is stable)
	Grade 3 ^b or 4 ^c	Permanently discontinue	
 Administer corticosteroids (initial dose of 1-2 mg/kg prednisone or equivalent) followed by taper 	
Type 1 diabetes mellitus (T1DM) or Hyperglycemia	New onset T1DM or Grade 3 or 4 hyperglycemia associated with evidence of β -cell failure	Withhold ^d	
 Initiate insulin replacement therapy for patients with T1DM Administer anti-hyperglycemic in patients with hyperglycemia 	
 Monitor patients for hyperglycemia or other signs and symptoms of diabetes.
Hypophysitis	Grade 2	Withhold	
 Administer corticosteroids and initiate hormonal replacements as clinically indicated. 	
 Monitor for signs and symptoms of hypophysitis (including hypopituitarism and adrenal insufficiency)
	Grade 3 or 4	Withhold or permanently discontinue ^d		
Hyperthyroidism	Grade 2	Continue	
 Treat with non-selective beta-blockers (eg, propranolol) or thionamides as appropriate 	
 Monitor for signs and symptoms of thyroid disorders

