	Grade 3 or 4	Withhold or permanently discontinue ^d		
Hypo-thyroidism	Grade 2, 3, 4	Continue	
 Initiate thyroid replacement hormones (eg, levothyroxine or liothyronine) per standard of care 	
 Monitor for signs and symptoms of thyroid disorders.
Nephritis: grading according to increase creatinine or	Grade 2	Withhold	
 Administer corticosteroids (prednisone 1-2 mg/kg or equivalent) followed by taper. 	
 Monitor changes of renal function
	Grade 3 or 4	Permanently discontinue		

irAEs	Toxicity grade or conditions (CTCAE V5.0)	Action with pembrolizumab	Corticosteroid and/or other therapies	Monitoring and follow-up
acute kidney injury				
Myocarditis	Grade 1 or 2	Withhold	• Based on severity of AE administer corticosteroids	
 • Ensure adequate evaluation to confirm etiology and/or exclude other causes
	Grade 3 or 4	Permanently discontinue		
All Other immune-related AEs	Persistent Grade 2	Withhold	• Based on severity of AE administer corticosteroids	
 • Ensure adequate evaluation to confirm etiology or exclude other causes
	Grade 3	Withhold or discontinue based on the event ^e		
	Recurrent Grade 3 or Grade 4	Permanently discontinue		

- a. AST/ALT: >3.0 - 5.0 x ULN if baseline normal; >3.0 - 5.0 x baseline, if baseline abnormal; bilirubin:>1.5 - 3.0 x ULN if baseline normal; >1.5 - 3.0 x baseline if baseline abnormal
- b. AST/ALT: >5.0 to 20.0 x ULN, if baseline normal; >5.0 - 20.0 x baseline, if baseline abnormal; bilirubin:>3.0 - 10.0 x ULN if baseline normal; >3.0 - 10.0 x baseline if baseline abnormal
- c. AST/ALT: >20.0 x ULN, if baseline normal; >20.0 x baseline, if baseline abnormal; bilirubin: >10.0 x ULN if baseline normal; >10.0 x baseline if baseline abnormal
- d. The decision to withhold or permanently discontinue pembrolizumab is at the discretion of the Investigator or treating physician. If control achieved or \leq Grade 2, pembrolizumab may be resumed.
- e. Events that require discontinuation include but are not limited to: Guillain-Barre Syndrome, encephalitis, Stevens-Johnson Syndrome and toxic epidermal necrolysis.

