9.5.3. Pembrolizumab Events of Clinical Interest

Selected non-serious and SAEs are also known as Events of Clinical Interest (ECI) for pembrolizumab, and must be reported to the Sponsor.

Events of clinical interest for this trial include:

1. an overdose of pembrolizumab, as defined in [Section 9.5.2](#), that is not associated with clinical symptoms or abnormal laboratory results.
2. an elevated AST or ALT lab value that is greater than or equal to 3X the ULN and an elevated total bilirubin lab value that is greater than or equal to 2X the ULN and, at the same time, an ALP lab value that is less than 2X the ULN, as determined by way of protocol-specified laboratory testing or unscheduled laboratory testing.*

*Note: These criteria are based upon available regulatory guidance documents. The purpose of the criteria is to specify a threshold of abnormal hepatic tests that may require an additional evaluation for an underlying etiology. The trial site guidance for assessment and follow up of these criteria can be made available. It may also be appropriate to conduct additional evaluation for an underlying etiology in the setting of abnormalities of liver blood tests including AST, ALT, bilirubin, and ALP that do not meet the criteria noted above. In these cases, the decision to proceed with additional evaluation will be made through consultation between the study Investigators and the Sponsor Medical Monitor. However, abnormalities of liver blood tests that do not meet the criteria noted above are not ECIs for this trial.

For dose modification and other guidelines related to events of interest for both pembrolizumab and futibatinib, please see [Section 5.3](#) of this protocol.

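### The planned liver-test shift tables (SAP 5.5.3) either mix two grading scales or understate rises when baseline AST, ALT or bilirubin is abnormal, because CTCAE v5.0 then grades against the patient's own baseline

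*SAP*

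**What the plan says.** SAP 5.5.3 grades laboratory results by NCI CTCAE Version 5.0. It then plans: "Shift tables will be presented for each laboratory parameter to display the shift from baseline grade to the worst post-baseline grade". SAP Table 11 includes AST, ALT and total bilirubin among the parameters. Worst grade is taken over all post-baseline assessments, including unscheduled ones. The section gives no rule for assigning a baseline grade when the baseline value is abnormal.

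The grade column of Protocol Table 8 is labelled CTCAE V5.0, and its footnotes a-c give the liver cut-points. For Grade 2 they read "AST/ALT: >3.0 - 5.0 x ULN if baseline normal; >3.0 - 5.0 x baseline, if baseline abnormal" and "bilirubin:>1.5 - 3.0 x ULN if baseline normal; >1.5 - 3.0 x baseline if baseline abnormal". For Grade 3 the transaminase rule is "AST/ALT: >5.0 to 20.0 x ULN, if baseline normal; >5.0 - 20.0 x baseline, if baseline abnormal". Grade 4 has the same two-way structure.

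Protocol 4.1 criterion 6d allows AST and ALT up to 2.5 x ULN at entry. It adds an exception, "if liver function abnormalities are due to underlying liver metastasis, AST and ALT", that raises the limit to 5.0 x ULN. Criterion 6e allows total bilirubin up to 1.5 x ULN, or 3.0 x ULN in Gilbert's syndrome.

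Two other liver rules in the protocol are on ULN: the Hy's Law criteria in 5.3.2, and the event of clinical interest in 9.5.3, whose first part is "an elevated AST or ALT lab value that is greater than or equal to 3X the ULN".

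**The concern.** A shift table is informative only if its rows and columns use the same scale and that scale shows the change of interest. For a patient with an abnormal baseline, the column (worst grade) is relative to that patient's own starting value. The row (baseline grade) could be set on ULN, which gives two scales in one table. It could instead be set on the own-baseline scale, on which every abnormal baseline equals 1.0 and carries no information. The SAP leaves the choice open, so programmers could take either.

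At stake is how hepatic safety reads in the study report for a combination in which the protocol sets liver rules for both drugs. A large absolute rise could be tabulated as stability or even recovery, and a stable abnormal value could appear as recovery. Time to resolution in SAP 5.5.3, if summarised, refers to the baseline grade and so inherits the same ambiguity.

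**Working it through.** The plan states no figure to reproduce. The check applies the plan's own cut-points to the baselines that entry allows.

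**Inputs.** Protocol Table 8 footnotes a-c: Grades 2, 3 and 4 start above 3, 5 and 20 for AST/ALT, and above 1.5, 3 and 10 for bilirubin. The unit is ULN if baseline is normal and own baseline if it is abnormal. Protocol 4.1 criteria 6d-e: AST/ALT up to 2.5 or 5.0 x ULN, bilirubin up to 1.5 or 3.0 x ULN.

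**Step 1: where grades start for an abnormal baseline.** Threshold in ULN units = cut-point x baseline multiple.
- ALT baseline 2.5 x ULN: Grade 2 above 3 x 2.5 = 7.5 x ULN; Grade 3 above 5 x 2.5 = 12.5 x ULN.
- ALT baseline 5.0 x ULN: Grade 2 above 3 x 5.0 = 15 x ULN; Grade 3 above 5 x 5.0 = 25 x ULN.
- Bilirubin baseline 3.0 x ULN: Grade 2 above 1.5 x 3.0 = 4.5 x ULN.

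So an ALT of at most 3.0 x baseline, or a bilirubin of at most 1.5 x baseline, is below Grade 2 whatever its absolute value.

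**Step 2: worked patients.** Worst value = baseline x ratio.

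| Test | Baseline (x ULN) | Ratio | Worst (x ULN) | Baseline grade on ULN | Worst grade, own-baseline rule | Worst grade on ULN |
|---|---|---|---|---|---|---|
| ALT | 2.4 | 2.9 | 6.96 | <=1 | <=1 | 3 |
| ALT | 4.5 | 2.9 | 13.05 | 2 | <=1 | 3 |
| ALT | 5.0 | 2.8 | 14.0 | 2 | <=1 | 3 |
| ALT | 4.5 | 1.0 | 4.5 | 2 | <=1 | 2 |
| Bilirubin | 1.4 | 1.45 | 2.03 | <=1 | <=1 | 2 |
| Bilirubin | 2.8 | 1.45 | 4.06 | 2 | <=1 | 3 |

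**Step 3: convention 1, baseline graded on ULN.** The table sets the fifth column against the sixth. Row 1 shows no worsening. Rows 2 and 3 show improvement although ALT nearly tripled. Row 4 shows improvement although nothing changed.

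**Step 4: convention 2, baseline graded against itself.** Every abnormal baseline has ratio 1.0 and is ungraded. All six patients then move to Grade 1 at most. The scale is consistent, but the first three ALT patients look mild although each is Grade 3 on ULN.

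**Assumption.** Table 8 starts at Grade 2, so the documents do not give the lower limit of Grade 1. It is taken to lie anywhere from just above 1.0 to 3.0 x baseline for AST/ALT, so the worst grade in the ALT rows is 0 or 1. Neither shows a worsening from a ULN-based Grade 1. If Grade 1 covers ratios up to 3.0, apparent improvement needs a baseline AST/ALT above 3 x ULN, which criterion 6d allows only with liver metastasis. On the same basis, apparent improvement in bilirubin needs a baseline above 1.5 x ULN, which criterion 6e allows only in Gilbert's syndrome.

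**The case against.** The strongest reply is that the SAP follows the protocol. The safety endpoint is defined by CTCAE v5.0 grades, and the protocol uses baseline-relative grades deliberately, since the pembrolizumab actions in Table 8 depend on them. Grading both time points against own baseline is a coherent measure of change from where the patient started. This stands in part: CTCAE v5.0 grading is not wrong, and the protocol does not put all its liver rules on ULN. But a coherent own-baseline table still does not show the ULN-level shift, and the SAP does not say which convention applies.

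The second reply is that nothing is lost. SAP 5.5.3 also plans descriptive statistics with maxima, change from baseline by scheduled visit and by-patient listings, and listings are readable in a trial of about 46 patients. Under Protocol 9.3.1, a laboratory abnormality with clinical impact becomes an adverse event. Cases meeting the 9.5.3 criterion must be reported to the sponsor. The safety reviews rest on the unacceptable-toxicity definition in Protocol 5.2, and no decision rule uses the shift table. A reader might infer that liver toxicity is concealed; the documents do not support that.

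What remains is a gap in summary. The by-visit statistics are in SI units from local laboratories with their own reference ranges (Protocol 6.2) and cover scheduled visits, so they do not tabulate peak multiples of ULN. Adverse events are graded on the same CTCAE scale, and events of special interest are groups of preferred terms (SAP 6.3). The public SAP text plans neither a ULN-based liver table nor a count of the 9.5.3 criterion. An isolated ALT rise, as in the worked cases, would not meet that combined criterion anyway.

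**Conclusion.** The point holds as a defect in one safety display. For AST, ALT and bilirubin with an abnormal baseline, neither available convention gives a shift table that shows the ULN-level change. Rises to at most 3.0 x baseline for AST/ALT, or 1.5 x baseline for bilirubin, stay below Grade 2. With baseline graded on ULN they can show as no change or, in restricted groups, as improvement. With baseline graded against itself they show as Grade 1 at most. The conclusion rests on the Table 8 cut-points and the stated range for the Grade 1 limit.

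Three stronger inferences are not supported:
- A near-tripling does not generally appear as improvement. That needs baseline graded on ULN and, if Grade 1 covers ratios up to 3.0, a baseline AST/ALT above 3 x ULN.
- The near-tripling does not carry over to bilirubin, where the limit is 1.5-fold.
- The number affected cannot be stated. The documents give no rate of abnormal baselines. An assumed 10-20% would be 2-4 of 20 patients per cohort, but that counts every abnormal baseline, and not all of them would be misread.

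The efficacy analysis and the safety decision rule are not touched.

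**What to change.** In SAP 5.5.3, for AST, ALT and total bilirubin only, build the shift table on one ULN-multiple scale at both baseline and worst post-baseline:
- AST/ALT: <=ULN, >1-3, >3-5, >5-20, >20 x ULN.
- Total bilirubin: <=ULN, >1-1.5, >1.5-3, >3-10, >10 x ULN.

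The upper boundaries are the baseline-normal cut-points of Table 8 footnotes a-c, applied to every patient. The ULN boundary is added because those footnotes begin at Grade 2. Label the categories as ULN multiples, not CTCAE grades.

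Report the CTCAE v5.0 worst grade for these tests in a separate, non-shift table, so that the protocol's safety endpoint is still delivered. Add a count of patients meeting the combined AST/ALT, bilirubin and ALP criterion of Protocol 9.5.3.

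The cost is SAP wording and one or two extra tables from data already collected. No clinical rule changes. The drawback is that small movements across a cut-point in patients with a high baseline, such as ALT from 4.9 to 5.1 x ULN, will show as a category shift, so the table should be read with the listings.
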